#### **6.1.4. Study Drug Dispensing**

Dosing of ataluren will be based on milligrams of drug per kilogram of subject body weight at screening/baseline (Visit 1) and will be adjusted to allow for dosing (as shown in [Table 2](#) and [Table 3](#)) with the available sachet dose strengths. A form (CRF) containing pertinent information for the subject's ataluren dispensing will be provided to the designated study pharmacy by the clinical site staff.

The designated study pharmacy (e.g., central pharmacy, pharmacist or other qualified person) will be responsible for dispensing study drug according to the Investigator's directions. The clinical site staff will contact the subject or parent(s)/caregiver(s) or legal guardian(s) to confirm availability to receive study drug shipment, including confirmation of receipt of study drug. Sufficient study drug will be provided for each study period at the beginning of the period.

Depending upon the magnitude of change in subject body weight since baseline, the number and type of sachets to be used by the subject may remain the same or may be adjusted.

#### **6.1.5. Return of Study Drug**

Subjects or parent(s)/caregiver(s) or legal guardian(s) should return all used and unused cartons and unused sachets of ataluren as instructed. Study drug dispensing to the subjects and the return of any unused study drug for compliance assessments will be documented.

#### **6.1.6. Storage and Stability**

Sachets containing ataluren will be shipped and stored at room temperature (~15 to 30°C). The available stability data from representative samples support the use of the drug product for 48 months when stored at room temperature.

#### **6.1.7. Study Drug Accountability**

Study drug must not be used outside the context of this clinical trial.

The investigator/site personnel and/or designated study pharmacy must maintain accurate records of the receipt of all ataluren shipped by the designated study pharmacy, including, but not limited to, the date received, lot number, amount received, amount returned, and the disposition of all study drug. Current reconciliation and dispensing records must also be maintained that include the date and, relevant lot number and number of cartons and sachets dispensed, and number of unused cartons and sachets returned, and subject's assigned study number.

Study drug must be returned to PTC Therapeutics designee, except where sites are required to destroy study drug per their local standard operating procedures.

#### **6.1.8. Overdose Precautions**

For any subject experiencing an overdose (administration of an ataluren dose >4 times the highest intended total daily dose level for this protocol [ $>160$  mg/kg/day]), observation for any symptomatic side effects should be instituted, and vital signs and biochemical and hematological parameters should be followed closely (consistent with the protocol or more frequently, as needed). Appropriate supportive management to mitigate adverse effects should be initiated. Pending the acquisition of sufficient human experience with the drug, use of gastric lavage or induction of emesis is not specifically recommended nor contraindicated.

The PTC Therapeutics medical monitor should be contacted if an overdose occurs. Under applicable regulations, overdosing may be considered a serious adverse event (SAE) and should be reported accordingly (see Section 8.9).

### **6.1.9. Inadvertent Exposure and Spill Precautions**

Reference can be made to the current ataluren [IB](#) for information on inadvertent exposures and spill precautions.

## **6.2. Study Drug Treatment**

### **6.2.1. Duration of Therapy**

The actual duration of ataluren treatment under this protocol will be subject to the following conditions:

- The subject has the right to withdraw consent and discontinue ataluren at any time.
- The subject's condition substantially worsens after initiating ataluren treatment. In such a case, the subject will be carefully evaluated by the investigator in consultation with the PTC Therapeutics medical monitor. The subject will be withdrawn from treatment if continuing would place them at risk.
- The investigator may withdraw the subject from ataluren treatment, if, in the investigator's clinical judgment, it is not in the subject's best interest to continue or if the subject is not complying with the protocol (ie, per protocol visits, return of unused study drug).
- If the subject is unable to tolerate ataluren, he will be withdrawn from treatment.
- The subject is eligible to participate in another ataluren nmDBMD clinical trial program initiated by PTC Therapeutics.
- This study is discontinued by the relevant regulatory authority and/or PTC Therapeutics.
- Ataluren becomes commercially available.

### **6.2.2. Schedule of Administration**

Three doses should be taken per day - the first dose in the morning (10 mg/kg), the second dose during the middle of the day (mid-day - 10 mg/kg), and the third dose in the evening (20 mg/kg). It is suggested that each dose should be taken within ~30 minutes after a meal.

### **6.2.3. Instructions for Delays in Dosing**

If a subject experiences a delay in the administration of ataluren of  $\leq 1$  hour, the planned dose should be taken with no changes to the subsequent dose schedules. For a subject who has a delay of  $> 1$  hour but  $\leq 4$  hours, the planned dose should be taken; however, all future doses for that day should be shifted later by an approximately corresponding amount. For a subject who has a delay in administration of ataluren of  $> 4$  hours, the dose should not be taken. Ataluren administration may continue but the missed dose should not be made up and the planned timing of subsequent ataluren dosing should not be altered.

#### **6.2.4. Study Drug Preparation and Storage**

For administration, the full contents of the sachet should be mixed with at least 30 mL (1 ounce) of liquid (water, milk, fruit juice, fruit punch) or 3 tablespoons of semi-solid food (yogurt, pudding, or applesauce) and administered with food. The prepared dose should be mixed well and stirred for approximately 30 to 60 seconds before administration. The amount of the liquid can be increased based on subject preference.

Each prepared dose is best administered immediately after preparation. The prepared dose should be discarded if not consumed within 24 hours of preparation (if kept refrigerated), or within 3 hours of preparation (if kept at room temperature).

The clinic staff will instruct each subject or parent/caregiver or legal guardian on the specific number of sachets to be taken for each dose and will provide detailed oral directions regarding drug preparation. In addition, detailed written drug mixing and dosing instructions will be provided to the subject or parent/caregiver or legal guardian when drug supplies are dispensed.

#### **6.3. Safety Monitoring and Study Drug Dose Interruption/Modification**

##### **6.3.1. Laboratory Abnormalities and Adverse Events Requiring Evaluation and Potential Drug Interruption/Modification**

Subjects must be monitored closely for AEs or laboratory abnormalities during the course of the study. Monitoring and capturing of AEs will be conducted approximately every 12 weeks through phone conversations (post-drug dispensing) or through visits to site.

For AEs or laboratory abnormalities, the investigator will use judgment in determining whether the event or abnormality is clinically significant, whether diagnostic evaluation is warranted, and whether potential interruption of ataluren treatment is appropriate. In general, life-threatening (Grade 4) or severe (Grade 3) AEs or laboratory abnormalities should be considered clinically significant, although recurrent or persistent moderate events (Grade 2) may also be considered clinically significant in certain circumstances. Reference should be made to the Common Terminology Criteria for Adverse Events (CTCAE), Version 5 (see [https://ctep.cancer.gov/protocoldevelopment/electronic\\_applications/docs/CTCAE\\_v5\\_Quick\\_Reference\\_8.5x11.pdf](https://ctep.cancer.gov/protocoldevelopment/electronic_applications/docs/CTCAE_v5_Quick_Reference_8.5x11.pdf)) for grading the severity of AEs and laboratory abnormalities.

If the subject experiences a dose-limiting AE related to ataluren, then drug administration can be paused, as necessary, until the AE resolves or stabilizes to an acceptable degree. If further evaluation reveals that the AE is not related to ataluren, treatment will be continued at the original dose level. The PTC Therapeutics Pharmacovigilance Department will be notified of any SAE or any AE that leads to dose reduction or treatment discontinuation.

Cases of decreased renal function have been observed in patients with nonsense mutation cystic fibrosis (nmCF) receiving ataluren and intravenous aminoglycosides together with other antibiotics for cystic fibrosis exacerbations (Section 6.4.1). As a precaution, Table 1 provides information on actions to be taken in the event that abnormalities are noted in specified renal laboratory parameters. Thresholds are provided for interrupting study drug immediately or for interrupting study drug after confirmation of a value beyond the threshold. For AEs or laboratory abnormalities not listed in Table 1, the investigator should use his/her judgment in determining whether the event or abnormality is clinically significant, whether diagnostic evaluation is warranted, and whether potential interruption of study drug is appropriate.

In general, life-threatening (Grade 4) or severe (Grade 3) AEs or laboratory abnormalities should be considered clinically significant, although recurrent or persistent moderate (Grade 2 events) may also be considered clinically significant in certain circumstances.

**Table 1: Renal Monitoring Parameters and Actions To Be Taken**

Laboratory Parameter	Stop Study Drug Immediately, Confirm Abnormal Value, and Then Start Work-Up	Stop Study Drug After Confirminga Abnormal Value, and Then Start Work-Up
Serum cystatin C	>2.00 mg/L	>1.33-2.00 mg/L
Serum creatinine	≥ Grade 2 (≥1.5 x ULN for age)	Grade 1 (>ULN - 1.5 x ULN for age)
Serum BUN	≥3.0 x ULN	≥1.5-3.0 x ULN

**Abbreviations:** BUN, blood urea nitrogen; ULN, upper limit of normal

aLaboratory abnormalities may be confirmed immediately or at the next scheduled clinic visit based on investigator judgment.

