**Table 2: Schedule of Events**

Study Period	Screening	Baseline	Treatment				6 Weeks Post D/C
Study Week (±7 Days)	Day 1 a	Day 1 a	Every 12 Weeks	Every 24 Weeks	Every 48 Weeks b	End of TX	
Informed consent c	X	X					
Clinical history d	X	X					
Vital signs	X				X	X	X
Height	X						
Weight	X	X		X e	X	X	X
Physical examination	X						
Hepatitis B and C f	X						
Hematology	X				X	X	X
Biochemistry	X				X	X	X
Drug dispensed		X	X g	X g	X g		
Pre-/post-shipment communication			X h	X h	X h		
Drug compliance			X i	X i	X i	X	
Adverse events	X	X	X i	X i	X i	X	X
Concomitant medication	X	X	X i	X i	X i	X	X

**Abbreviations:** D/C, discontinuation; TX, treatment

a Subjects who have not participated in an ataluren study in the past year are required to complete all assessments identified under screening. Subjects who have participated in an ataluren study within the past year only need to complete the assessments identified under baseline.

b Annual visits will occur every 48 weeks (ie, Weeks 48, 96, 144, 192, 240, 288, 336, 384, 432, 480, 528, 576, 624, 672, 720, etc).

c Informed consent will be signed before any study procedures are performed.

d Clinical history will be collected for ataluren-naïve subjects (siblings). For subjects enrolling from another ataluren clinical study, only clinical history reported since the last dose of ataluren in the prior DBMD study will be collected.

e Reminders will be communicated prior to every 24 week visit for subject to obtain a weight check-in between the annual visits at sites. This communication will be documented in the source.

f Hepatitis B and C testing is only required for ataluren-naïve subjects (siblings) or subjects who have a temporary treatment gap of 1 year before entering Study 016.

g Drug will be dispensed to the subject every 12 weeks.

h Clinical site staff will contact the subject or parent(s)/legal guardian(s) to confirm details and timing of the upcoming study drug shipment. Post-shipment contact will confirm receipt of and condition of study drug.

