i Subjects or parent(s)/caregiver(s) or legal guardian(s) should return all used and unused cartons and unused sachets of ataluren as instructed in order to assess study drug compliance.

j Clinical site staff will contact subject or parent(s)/legal guardian(s) every 12 weeks (by phone, email, or text if there is no clinic visit) to assess adverse events and concomitant medications.

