**Table 3: Schedule of Events for PTC124-GD-048-DMD Subjects**

Study Period Study Week (±7 Days)	Scr/Baseline Day 1 a	Treatment						6 Weeks Post D/C
		Week 14 b	Week 28 b	Week 40 Through End of TX				
				Every 12 Weeks c	Every 24 Weeks c	Every 48 Weeks c	End of TX	
Informed consent d	X							
Clinical history e	X							
Vital signs	X		X			X	X	X
Height	X	X	X					
Weight	X	X	X		X f	X	X	X
Physical examination	X							
Hepatitis B and C g	X							
Hematology		X	X			X	X	X
Biochemistry		X	X			X	X	X
Drug dispensed	X	X h	X h	X i	X i	X i		
Pre-/post-shipment communication		X		X i	X i	X i		
Drug compliance	X	X	X	X k	X k	X k	X	
Adverse events	X	X	X	X l	X l	X l	X	X
Concomitant medication	X	X	X	X l	X l	X l	X	X
PDMS-2	X	X	X					

**Abbreviations:** D/C, discontinuation; PDMS-2, [Peabody Developmental Motor Scale](#), second edition; Scr, screening; TX, treatment

a Screening/baseline (Day 1) of the current study may be the same day as visit 5 (Week 24) in Study [PTC124-GD-048-DMD](#), in which case, corresponding assessments in the two studies do not need to be repeated.

b Weeks 14 and 28 of the current study represent 38 and 52 weeks, respectively, of ataluren treatment for these Study 048 subjects.

c After the Week 28 visit, assessments will be conducted as outlined in the table every 12 weeks, every 24 weeks, and every 48 weeks. These visits will be anchored by the visit date for Week 28. The visit following Week 28 should be the first every 12 week visit at approximately Week 40 post-enrollment. Annual visits will occur every 48 weeks (ie, Weeks 76, 124, 172, etc).

d Informed consent will be signed before any study procedures are performed.

e Clinical history reported since the last dose of ataluren in Study 048 will be collected.

f Reminders will be communicated prior to every 24 week visit for subject to obtain a weight check-in between the annual visits at sites. This communication will be documented in the source.

g Hepatitis B and C testing is only required for ataluren-naïve subjects (siblings) or subjects who have a temporary treatment gap of 1 year before entering Study 016.

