#### **7.2.1.2. Treatment Visits during Study**

Study visits will occur every 12 weeks, 24 weeks, and 48 weeks during the treatment period. The subject is required to complete a visit at the clinical research facility every 48 weeks. Every 24 weeks, the subject is required to have a weight check. A study drug shipment will be sent to the subject/caregiver's home every 12 weeks. Clinical site staff will contact the subject (pre-and post-study drug dispensing) to notify of upcoming study drug shipment and to confirm study drug receipt. Phone conversations will be conducted to monitor and capture AEs and use of concomitant medications.

Subjects previously enrolled in [PTC124-GD-048-DMD](#) will complete 2 additional visits as indicated in [Table 3](#). Subjects will report to the clinical research facility for a Week 14 and Week 28 visit. After the Week 28 visit, study visits will follow the 12 weeks, 24 weeks, and 48 weeks schedule.

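### Table 1 lets confirmation of an intermediate renal value wait until the next scheduled clinic visit, which is usually 48 weeks away, with study drug continuing meanwhile

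*Protocol*

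**What the plan says.** Section 6.3.1 of the protocol sets a two-tier renal rule: "Thresholds are provided for interrupting study drug immediately or for interrupting study drug after confirmation of a value beyond the threshold". Table 1 gives the bands. In the upper band, drug stops at once. In the intermediate band, stopping and work-up both follow confirmation. Footnote a governs the timing: "Laboratory abnormalities may be confirmed immediately or at the next scheduled clinic visit based on investigator judgment".

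The length of that option depends on the visit schedule:

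- Section 7.2.1.2: "The subject is required to complete a visit at the clinical research facility every 48 weeks". Table 2, footnote b agrees: "Annual visits will occur every 48 weeks".
- During treatment, Table 2 marks biochemistry only at the 48-week visits and at End of Treatment. Section 7.2.2.7 shows that this panel contains all three Table 1 analytes.
- The 24-week item is a weight check: "Reminders will be communicated prior to every 24 week visit for subject to obtain a weight check-in between the annual visits at sites".
- The 12-week contacts cover adverse events and concomitant medications and may be made "by phone, email, or text if there is no clinic visit".
- Study 048 subjects (Table 3) have site visits with biochemistry at Weeks 14 and 28, then every 48 weeks: "These visits will be anchored by the visit date for Week 28".

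Section 6.3.1 also states a general duty: "Subjects must be monitored closely for AEs or laboratory abnormalities during the course of the study".

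**The concern.** Renal function is the only organ system for which this protocol sets numeric stopping thresholds. In the intermediate band the stopping action hangs on a confirmation that a compliant site may leave to the next annual visit, while drug continues to be dispensed every 12 weeks.

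Two consequences follow. First, subjects may go on being dosed for most of a year with an unexplained renal abnormality. Section 6.4.2 names a potential risk of renal dysfunction when subjects on ataluren become dehydrated, so the worry is not confined to antibiotic courses. Second, a repeat taken about 11 months later confirms little. A normal result leaves the earlier value unexplained, and an abnormal one cannot separate a persistent change from a new event.

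Deferral can also delay other steps. Section 6.3.2 expects the sponsor's medical monitor to be told of abnormalities that lead to interruption, and earlier contact is only encouraged. Under Section 8.1.1, a laboratory value that prompts nothing more than a confirmatory repeat need not be reported as an adverse event.

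**Working it through.** **Inputs.** Visit interval of 48 weeks (Section 7.2.1.2; Table 2, footnote b). Visit window of ±7 days (Tables 2 and 3). Study 048 visits at Weeks 14, 28, 76, 124 and 172 (Table 3 and footnote c). Planned enrolment of about 270 (Section 3).

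**Check of the schedule.** The annual visits listed in Table 2 (Weeks 48, 96, 144 and so on) are 48 weeks apart: 96 − 48 = 48. Those in Table 3 after Week 28 are too: 76 − 28 = 48 and 124 − 76 = 48.

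**Longest permitted wait, sample to sample.** Days = weeks between visits x 7.

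| Value flagged at | Next scheduled site visit with biochemistry | Nominal wait | With windows |
|---|---|---|---|
| Annual visit, Table 2 | 48 weeks later | 48 x 7 = 336 days | 336 − 14 = 322 to 336 + 14 = 350 |
| Week 14, Study 048 | Week 28 | (28 − 14) x 7 = 98 days | 98 − 14 = 84 to 98 + 14 = 112 |
| Week 28, Study 048 | Week 76 | (76 − 28) x 7 = 336 days | 336 − 7 = 329 to 336 + 7 = 343 |
| Week 76 or later, Study 048 | 48 weeks later | 336 days | 322 to 350 |

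The wider ranges allow ±7 days at both visits. The Week 28 row uses one window only, because later visits are anchored to the actual Week 28 date. In months, 336 / (365.25 / 12) = 11.04, with a range of 10.58 (322 days) to 11.50 (350 days). An unscheduled repeat or an End-of-Treatment visit shortens any of these.

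**Could an earlier visit count?** Section 7.2.1.2 also speaks of study visits every 12 and 24 weeks. If a site treated one of these as the next clinic visit, the wait would be 12 x 7 = 84 or 24 x 7 = 168 days. Neither has to take place at the clinic and neither carries scheduled biochemistry, so footnote a does not oblige a site to read it that way.

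**Does another provision set an earlier retest?**

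- Sections 6.3.1 and 6.3.2 require close monitoring and testing guided by clinical judgment, without a date.
- Section 6.3.3 calls for interruption on an unacceptable laboratory abnormality, again without a retest date.
- Section 6.4.2 asks for particular vigilance when there is laboratory evidence of dehydration, also undated.
- Section 6.4.1 does date its creatinine and BUN tests (at least twice weekly), but only during IV aminoglycoside or vancomycin courses, when study drug is already interrupted.

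**Load of a dated retest.** The documents do not say how often intermediate values occur. Assuming 1%, 5% or 10% of 270 subjects are flagged in a 48-week round, with one repeat each: 270 x 0.01 = 2.7, 270 x 0.05 = 13.5, 270 x 0.10 = 27. That is about 3, 14 or 27 draws. The added load would be smaller, because some sites would already confirm at once.

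**The case against.** The strongest reply is that this is a deliberate choice. The table is tiered, the upper band stops drug at once, and the intermediate band offers immediate confirmation first and leaves timing to the investigator, in keeping with the rest of Section 6.3. The 11-month wait arises only if an investigator who is under a duty of close monitoring sees an abnormal renal value and decides to wait. Table 1 is described as a precaution, prompted by cases in cystic fibrosis patients on IV aminoglycosides, and that setting has its own controls. All of this stands, and it limits the weight of the point. It does not supply a retest date.

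Three stronger readings are tempting, and the documents do not support them:

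- **That the delay has no limit.** The next scheduled clinic visit is itself the limit, and the schedule dates it. The limit is long, not absent.
- **That every other safeguard is discretionary or driven by symptoms.** Close monitoring in Section 6.3.1 is worded as mandatory, and Section 6.4.2 has a laboratory trigger that a raised BUN or creatinine could meet.
- **That subjects are being harmed, or that the safety results are compromised.** The documents show no harm from delayed confirmation in nmDBMD, and no endpoint or analysis depends on footnote a.

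It can also be said that little study time may remain. If the planned duration of about 13 years runs from the original protocol date of 08 Oct 2010 (an assumption, since first enrolment is not given), it ends about 695 days after the current version of 12 November 2021. That is 695 / 336, or roughly two annual rounds. Table 2 lists visits to Week 720 and beyond, so the horizon is uncertain. A short remainder reduces the benefit but does not remove the gap.

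**Conclusion.** The point holds as a **cheap improvement**. For intermediate renal values, a site that follows the protocol exactly may continue dosing for up to about 336 days (322-350 with windows) before confirming. The exception is 98 days (84-112) for Study 048 subjects flagged at Week 14.

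This rests on two readings of the text: that the next scheduled clinic visit means the required 48-week site visit, and that the ±7-day window applies at both visits except where Table 3 anchors to Week 28. It describes what is permitted. How often intermediate values occur, and how often sites defer, cannot be learned from the documents, so the size of the safety benefit cannot be estimated.

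**What to change.** In Table 1, footnote a, replace the option to wait for the next scheduled clinic visit with a dated requirement. For example: an abnormal value must be confirmed by a repeat sample, unscheduled if necessary, within a fixed number of weeks of the result. The clinical team should set the number; 2-4 weeks (14-28 days) is an illustration and is not taken from the documents. Keep the 48-week visit schedule, the immediate-stop band and the investigator's discretion over further evaluation.

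The cost is one footnote and a memo to sites, with the change carried in a protocol amendment. In practice it means some unscheduled repeat draws in flagged subjects (about 3 to 27 per 48-week round under the assumed 1-10% rates), with central-laboratory shipping and travel for subjects, some of whom are nonambulatory. An 8-hour fast would be added if the rule for scheduled biochemistry in Section 7.2.2.7 is applied to the repeats.

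### Table 1 lets confirmation of a moderately abnormal renal value wait for the next clinic visit, up to 48 weeks away, while dosing continues; two boundary values also sit in both action columns

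*Protocol*

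**What the plan says.** Protocol Section 6.3.1 opens with a general duty: "Subjects must be monitored closely for AEs or laboratory abnormalities during the course of the study". Table 1 in that section then gives specific renal rules in two columns. Values in the first column stop drug at once, before confirmation. Values in the second column stop drug only after confirmation: cystatin C above 1.33 and up to 2.00 mg/L, creatinine above ULN and up to 1.5 x ULN, and BUN from 1.5 to 3.0 x ULN. Footnote a, attached to the second column, says: "Laboratory abnormalities may be confirmed immediately or at the next scheduled clinic visit based on investigator judgment". It sets no outer limit.

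The visit calendar is in Section 7.2.1.2: "The subject is required to complete a visit at the clinical research facility every 48 weeks". Table 2 agrees: "Annual visits will occur every 48 weeks (ie, Weeks 48, 96, 144, 192" and so on. The 24-week item is described as follows: "Reminders will be communicated prior to every 24 week visit for subject to obtain a weight check-in between the annual visits at sites". The intermediate contacts take place "every 12 weeks (by phone, email, or text if there is no clinic visit) to assess adverse events and concomitant medications". For subjects from Study 048, Table 3 has visits at Weeks 14 and 28 and then the same cycle: "Annual visits will occur every 48 weeks (ie, Weeks 76, 124, 172, etc".

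The first-column creatinine threshold is "≥ Grade 2 (≥1.5 x ULN for age"). The second-column range for creatinine ends at the same 1.5 x ULN.

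**The concern.** A rule that stops drug after confirmation works only if confirmation comes soon. Footnote a ties it, at the investigator's option, to the clinic calendar, and that calendar is annual. Table 1 was added as a precaution after decreased renal function was seen in cystic fibrosis patients receiving ataluren with intravenous aminoglycosides. Section 6.4.2 also warns of renal dysfunction during dehydration in subjects on ataluren. If confirmation waits for the next visit, the rule cannot act for most of a year on the values it was written to catch.

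The boundary question is separate and smaller. Where one measured value meets the conditions of both columns, the table gives two different instructions and no text says which prevails.

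**Working it through.** **Inputs**
- Confirmation timing: immediately or at the next scheduled clinic visit (Table 1, footnote a).
- Clinic visit interval: 48 weeks (Section 7.2.1.2; Table 2).
- Visit window: ±7 days (Table 2 header).
- On-treatment biochemistry in Table 2: the 48-week visits and End of Treatment only. Section 7.2.2.7 puts BUN, creatinine and cystatin C in that panel.
- Doses: three per day (Section 6.2.2). Drug supply: every 12 weeks (Table 2).

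**Permitted wait, Table 2 subjects**
- All the annual visits listed in Table 2, Weeks 48 to 720, are 48 weeks apart, which reproduces the stated interval.
- 48 x 7 = 336 days.
- With the window at both ends: 336 - 14 = 322 days to 336 + 14 = 350 days.
- Scheduled doses over the nominal interval: 336 x 3 = 1,008.
- Drug supplies dispensed: 48 / 12 = 4.

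**Alternative readings of the next scheduled clinic visit**

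| Reading | Wait |
|---|---|
| Required visit every 48 weeks | 336 days |
| 24-week weight check counted as a clinic visit | 24 x 7 = 168 days |
| 12-week contact held on site | 12 x 7 = 84 days |

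The last two readings are weaker. Neither contact has to be at the clinic, and neither has scheduled biochemistry.

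**Study 048 subjects (Table 3)**
- A value first seen at Week 14 can wait until Week 28: 14 x 7 = 98 days.
- A value first seen at Week 28 can wait until Week 76: 76 - 28 = 48 weeks = 336 days. Later gaps (76 to 124, 124 to 172) are also 48 weeks.

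**Does other text shorten the wait?**
- Section 6.3.1 calls Grade 3 and 4 abnormalities clinically significant in general, and recurrent or persistent Grade 2 in some circumstances. The second-column creatinine range is Grade 1, so this language does not reach it.
- Section 6.3.2 asks for the medical monitor to be notified when an abnormality leads to dose interruption. A deferred second-column value has led to none.
- Section 8.1.1 excludes from AE reporting a laboratory abnormality that needs nothing beyond a confirmatory repeat, so the 12-weekly AE contact would not be expected to pick it up.

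**Boundary values**

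| Parameter | Stop immediately | Stop after confirming | Values in both |
|---|---|---|---|
| Cystatin C (mg/L) | >2.00 | >1.33 to 2.00 | none |
| Creatinine (x ULN) | ≥1.5 | >1 to 1.5 | 1.5 |
| BUN (x ULN) | ≥3.0 | ≥1.5 to 3.0 | 3.0 |

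A check of each row in steps of 0.01 found exactly these two shared values, reading the upper end of each range as included.

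**The case against.** The footnote permits delay and does not require it. Immediate confirmation is the first option named, and Sections 6.3.1 and 6.3.2 leave testing and interruption to clinical judgment and encourage contact with the medical monitor. The 48 weeks comes from combining two tables, and the dose count describes the worst case without measuring risk. Results come from a central laboratory, so dosing on a known abnormality starts somewhat after the draw. The deferral covers only the milder tier. The setting that prompted Table 1 also has its own controls: ongoing IV aminoglycoside or vancomycin is excluded at entry (Section 4.3), and during a course drug is interrupted, with creatinine and BUN measured at least twice weekly (Section 6.4.1).

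All of this stands as a limit on how often and how seriously the gap would matter. It does not close the gap. None of the general text sets a deadline, and Section 6.3.1 reserves open investigator judgment for abnormalities outside Table 1, whereas footnote a brings it back for the timing of confirmation inside the table. The antibiotic rules do not cover a subject whose renal values drift without such a course.

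On the boundaries, a reader would probably let the explicit ≥ under the immediate-stop heading prevail. That is a sensible guess, but the table does not say it, and the cystatin C row shows how a clean split is written.

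**Conclusion.** The point holds. Followed as written, Table 1 allows dosing to continue on an unconfirmed second-column renal value for up to 336 days (322 to 350 with windows) under Table 2. For Study 048 subjects the limit is 98 days for a value first seen at Week 14, and 48 weeks from Week 28 onward. These are maxima. They assume that the investigator takes the deferral option, that no unscheduled test is done, and that the next scheduled clinic visit means the required 48-week visit. The protocol gives no information on how often that would happen. First-column values are unaffected because drug stops before confirmation.

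The overlap at creatinine 1.5 x ULN and BUN 3.0 x ULN is a real contradiction in a stopping threshold, but it concerns two single values and would affect few subjects. The first point should be corrected, and the second can be tidied in the same amendment.

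**What to change.** Reword footnote a so that a second-column value is confirmed by an unscheduled repeat test within a short fixed window, and delete the option to wait for the next scheduled clinic visit. The protocol offers no figure for the window, so the sponsor's clinicians should set it. In the second column, end the creatinine range at <1.5 x ULN and the BUN range at <3.0 x ULN, so that each value has one action.

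The change is one footnote and two inequality signs. The practical cost is an occasional extra blood draw, which footnote a already allows.
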